### **5.4 Programming Specifications**

The programming specifications, including the mock-up analysis tables, figures, and data listings, as well as the derived database specifications, will be prepared in stand-alone documents. The programming specification documents will be finalized prior to database lock.

## **6 ANALYSIS OF DISPOSITION AND SUBJECT CHARACTERISTICS**

### **6.1 Disposition and Analysis Populations**

Subject disposition information will be summarized. Counts (number and percent) of subjects who are randomized, who are dosed with study medication, who complete the study, and who withdraw early from the study will be presented. The primary reasons for early withdrawals will

also be tabulated. The SP will be used as the denominator for the percentage calculation. Subject disposition, inclusion / exclusion criteria and comments will be listed.

The number and percent of patients in each analysis population will also be tabulated.

## **6.2 Demographics and Baseline Characteristics**

Demographics and baseline characteristics will be summarized descriptively for the Safety population and for FAS population, if it differs from the SP.

Demographic and baseline characteristics include, but are not limited to, age at informed consent, gender, race, ethnicity, height, baseline weight, and baseline body mass index. Continuous variables (e.g., age, weight, etc.) will be summarized by descriptive statistics. Categorical variables (e.g., gender, race, and ethnicity) will be summarized by the number and percentage of patients in corresponding categories. Demographic characteristics will also be listed.

Medical/surgical history will be summarized for the number and percentage of patients for each system organ class and preferred term. Medical history will also be listed.

Genetic testing results for the HoFH genotype mutational status will be listed by patient.

## **6.3 Concomitant Medications**

All medications administered during the study will be listed and coded using the most current version of the World Health Organization (WHO) Drug Reference List. A listing of all prior and concomitant medications including the reported term, preferred term, and Anatomical Therapeutic Chemical (ATC) class, start and stop dates, and other relevant data will be provided for the SP. Concomitant medications include all medications taken on or after the date of the first dose of study drug. Prior medications include all medications taken before the date of the first dose of study drug and discontinued before the first dose of study drug.

# **7 ANALYSIS OF EFFICACY**

The following efficacy assessments will be measured in order to obtain the primary, secondary, and exploratory endpoints:

- Fasting LDL-C, non-HDL-C, TC, TG, HDL-C, and VLDL-C at baseline, Day 14, Day 28, Day 42, Day 56, Day 70, and Day 84 (or the ET Visit, if applicable);
- Fasting ApoB, ApoA-I, ApoA-II, ApoC-II, ApoC-III, ApoE, and Lp(a) at baseline, Day 28, Day 56, and Day 84 (or the ET Visit, if applicable);
- hsCRP at baseline, Day 28, Day 56, and Day 84 (or the ET Visit, if applicable);
- Fibrinogen at baseline, Day 28, Day 56, and Day 84 (or the ET Visit, if applicable); and
- **Cl**

Given the proposed crossover design of this study, a within-patient analysis can be performed for the comparison of dose groups. For continuous variables, the dose groups will be compared on their change and percent reduction from baseline (using their pre-treatment baseline value). For binary variables such as the percentage of patients, descriptive statistics will be calculated for each dose group.

Baseline lipid measurements will be defined as the average of the last two fasting measurements prior to the first dose of study medication. If only one measurement is available then this measurement will be used as baseline. Baseline for all other efficacy variables will be the last measurement prior to the first dose of study medication.

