5.3 Randomization and Blinding

This is an open-label study, therefore, no randomization or blinding is necessary.

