### 2.2 Trial Design

This is a Phase 2, open-label, dose-finding, 3-period, 3-treatment study using successively escalating doses of 300 mg, 600 mg, and 900 mg gemcabene in patients with HoFH. All patients will be on each of the successive doses for 4 weeks at a time. Patients will remain on their current

stable, lipid-lowering therapy throughout the study. Patients will not be allowed in the study if they are undergoing apheresis or taking mipomersen or lomitapide.

The population for this study is male and female patients,  $\geq 17$  years of age, diagnosed with HoFH by genetic confirmation or a clinical diagnosis based on either (1) a history of an untreated LDL-C concentration  $>500$  mg/dL (12.92 mmol/L) together with either appearance of xanthoma before 10 years of age, or evidence of heterozygous familial hypercholesterolemia in both parents or, if history is unavailable, (2) LDL-C  $>300$  mg/dL (7.76 mmol/L) on maximally tolerated lipid-lowering drug therapy. Approximately 8 patients will be enrolled into the study. Total study duration will be up to 18 weeks and will consist of a Screening Visit, a Treatment Period, and a Follow-up Visit.

The Treatment Period is a sequential design whereby each patient will receive gemcabene 300 mg QD for 4 weeks. The same patients will then receive a 600 mg dose QD for 4 weeks and finally 900 mg dose QD for 4 weeks. There will be no interruptions in gemcabene dosing when changing from the 300 mg to the 600 mg dose or when changing from the 600 mg to the 900 mg dose unless there are clinically significant safety issues resulting in the temporary or permanent discontinuation of study drug. The first 300 mg dose of study drug will be administered at the site on Day 1. Assessments will be performed after the patient has been on the study drug for 2 weeks for each dosing level and on the last day of each dose.

The Follow-up Visit will occur 4 weeks ( $\pm 3$  days) after the last dose of study drug.

The schedule of events for the trial is provided in Table 1.

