### 7.1 Primary Efficacy Analysis

Descriptive statistics of the percent change from baseline in LDL-C will be presented by treatment group at each visit, with the focus being on the percent change from baseline to Day 28, Day 56, and Day 84 in LDL-C, using the FAS. A longitudinal analysis will be performed with a mixed-effects model repeated measures analysis including percent change in LDL-C as the dependent variable, visit as a fixed effect and patient as a random effect. The additional drug benefit with increasing dose will be estimated from the mixed-effects model. The FAS will be used for this analysis. Least-squares mean differences and corresponding 95% confidence intervals, separately for each of the 3 paired comparisons (300 versus 600 mg, 300 versus 900 mg, and 600 versus 900 mg) will be provided.

The mixed-effect model repeated measures analysis will use an unstructured covariance matrix for the within-subject correlation; if the model does not converge with this correlation structure, an auto-regressive correlation structure will be assumed. If the model still does not converge then other covariance structures will be explored. The final correlation structure will be determined by the information criteria of Akaike and Schwarz. The data from each scheduled visit will be included in the model. Example SAS® code for performing this analysis is as follows:

```
PROC MIXED;
  CLASS SUBJID VISIT;
  MODEL PCHG = VISIT;
  REPEATED VISIT / type=UN subject=SUBJID;
  LSMEANS VISIT / cl pdiff;
RUN;
```

In addition, a scatterplot with a linear regression fit of the percent reduction from baseline versus dose will be performed.

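### The SAP calls one fixed 300-600-900 mg sequence a crossover and reads visit differences as drug benefit of dose, although dose cannot be separated from time on treatment

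*SAP*

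**What the plan says.** The justification for comparing doses is in SAP 7: "Given the proposed crossover design of this study, a within-patient analysis can be performed for the comparison of dose groups". Doses are compared on change and percent reduction "using their pre-treatment baseline value".

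SAP 7.1 gives the model as "MODEL PCHG = VISIT", with an unstructured covariance matrix within patient, and adds: "The data from each scheduled visit will be included in the model". It interprets the result as follows: "The additional drug benefit with increasing dose will be estimated from the mixed-effects model". Least-squares mean differences with 95% confidence intervals are to be given for 300 v 600, 300 v 900 and 600 v 900 mg. In addition, "a scatterplot with a linear regression fit of the percent reduction from baseline versus dose will be performed".

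The crossover label and the drug-benefit sentence also stand in the Protocol Synopsis (Statistical Analyses) and Protocol 10.2.1.

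The design is described differently elsewhere. SAP 2.2 says: "The Treatment Period is a sequential design whereby each patient will receive gemcabene 300 mg QD for 4 weeks". The same patients then move to 600 mg and finally to 900 mg, with no planned break. Protocol 5.1 gives the same order for everyone, and Protocol 5.3 says: "This is an open-label study, therefore, no randomization or blinding is necessary". SAP 12 reports a renamed analysis population and no change of method.

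**The concern.** A crossover balances treatment against period by giving different patients different orders. Here there is one order, so nothing balances dose against time on treatment. Anything that moves LDL-C between Day 28 and Day 84 enters the dose comparisons: a response to the first dose that is still developing, changes in diet or adherence, or drift under background therapy.

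The SAP says the model estimates drug benefit from increasing dose, and nowhere limits that reading. SAP 7.1 is the primary efficacy analysis, SAP 7.2 applies similar analyses to the continuous secondary endpoints, and one secondary objective is to confirm the Phase 3 dose. A report that follows this text could present a difference between visits as a dose-response result.

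**Working it through.** SAP 11 gives no standard deviation, effect size or target interval width, so the plan has no figure on this point to reproduce. The check concerns the structure of the design.

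**Inputs.** Sequence and period length: Protocol 5.1, SAP 2.2. Lipid visits at Day 14, 28, 42, 56, 70 and 84: SAP Table 1. Primary visits at Day 28, 56 and 84: SAP 3.1.1. Model: SAP 7.1. Eight patients: SAP 11.

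**Which visits carry the dose labels.** Protocol 3.1 uses the last LDL-C value at each dose, and SAP 7.1 focuses on Day 28, 56 and 84. So 300 v 600 mg is Day 56 v 28, 300 v 900 mg is Day 84 v 28, and 600 v 900 mg is Day 84 v 56.

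**Three visits.** Dose (1, 2, 3 in units of 300 mg) and day (28, 56, 84) correlate 1.00. Intercept + dose + day has rank 2 of 3 columns. With 8 patients, patient + visit + dose as class factors has 8 + 2 + 2 = 12 columns and rank 10, so both dose parameters are aliased with visit.

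**Six visits.** With visit as a class factor, as the SAP specifies, intercept + visit + dose has 1 + 5 + 2 = 8 columns and rank 6. Dose is still fully aliased. Forcing time to be linear would make the two separable, with dose-day correlation 8/√(4 × 17.5) = 0.956. That also requires each dose's effect to be complete by its two-week visit. The SAP does not plan that model, and it is not proposed here.

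**What a dose comparison contains.** Write the mean percent change at a visit as a dose part D plus a time part T. Then

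Day 84 − Day 28 = [D(900) − D(300)] + [T(84) − T(28)].

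The data give only the sum. It equals the dose effect if T does not change, which needs response complete by week 4 of each dose and no drift. Protocol 3.1 assumes steady state at 28 days for plasma concentration; no passage assumes it for LDL-C.

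**Illustration only.** The drift d (points per week) is assumed; the documents contain no data on it, and its sign is unknown.

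| Comparison | Weeks apart | Shift | d = ±0.25 | d = ±0.5 |
|---|---|---|---|---|
| 300 v 600 mg | 4 | 4d | ±1 | ±2 |
| 600 v 900 mg | 4 | 4d | ±1 | ±2 |
| 300 v 900 mg | 8 | 8d | ±2 | ±4 |

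No dose effect with d = −0.5 gives Day 84 − Day 28 = −4 points. A true −2 points per dose step with no drift gives −2 × 2 = −4 as well. The planned Day 28, 56 and 84 means would be identical. For scale, Protocol 5.2 quotes −24% at 300 mg and −28% at 900 mg from a completed study, also a difference of −28 − (−24) = −4 points. The match with d = −0.5 comes from the value chosen for d and is not evidence of drift.

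**What the planned output can show.** Six visits give 6 × 5/2 = 15 pairwise contrasts. Three are within a dose: Day 28 v 14, 56 v 42 and 84 v 70. Values near zero would support a settled response without drift, though late response and opposite drift could cancel. Values away from zero would be a warning but not proof, since response may be complete at week 4 without being complete at week 2.

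**The case against.** The case for the plan is substantial:

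- A within-patient analysis is possible in a single-sequence trial, so the sentence in SAP 7 is wrong only in the word crossover. This stands. A reader might infer that the repeated-measures analysis is invalid; it is not.
- Both documents describe the sequence openly and say there is no randomization, so the design is not hidden. This stands, but the description does not correct SAP 7.1, which says what the model estimates.
- No test or decision rule uses the increments. The 15% definition uses each dose's mean reduction, and dose confirmation also draws on PK, safety, completed studies and the planned randomized study GEM-301 (Protocol 2.2 and 3.1). This stands and limits the impact. A reader might infer that the dose decision is unsound; the documents do not support that.
- The drift example rests on chosen values, and the 4-point benchmark comes from hypercholesterolemic patients on statins, not HoFH. This stands. The example shows how the shift scales, not how large it is.
- The within-dose contrasts are already in the planned output and partly probe the missing assumptions. This stands, although with 8 patients they are imprecise.

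**Conclusion.** Wrong as written; modest severity. The plan credits the design with a property it lacks and names as drug benefit a quantity in which dose and time on treatment cannot be told apart. The aliasing is exact under the planned model. It rests only on the fixed sequence and on visit as a class factor, not on any assumed number. The size and direction of any resulting bias are unknown: 8d for 300 v 900 mg and 4d for adjacent doses, with d not given in the documents.

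No estimate, confidence interval or decision rule changes. What changes is the conclusion that the three differences and the dose regression can carry. A reader might go further and infer that drift occurred, or that the dose trend is overstated. The documents support neither, since the bias could equally hide a dose effect.

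A separate limit applies to each dose's own mean reduction. It is measured against an uncontrolled pre-treatment baseline, and at 600 and 900 mg it follows 8 and 12 weeks of cumulative treatment.

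**What to change.** Make these changes before database lock, as SAP 1 allows, with the reason given in the CSR. After lock, put the same statements in the CSR.

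1. SAP 7: replace *crossover design* with *fixed-sequence dose escalation*.
2. SAP 7.1: replace the drug-benefit wording with *additional change from baseline after each dose step*. Label the three differences by visit as well as dose (Day 56 v 28, Day 84 v 28, Day 84 v 56). State there, and on the dose regression plot, that dose is confounded with time on treatment.
3. Present the within-dose contrasts (Day 28 v 14, 56 v 42, 84 v 70) beside the dose comparisons, described as an imprecise check for incomplete response or drift.
4. State that the 600 and 900 mg reductions follow 8 and 12 weeks of cumulative treatment against an uncontrolled baseline. Leave the 15% definition as it is.
5. SAP 12: record that this wording supersedes the Protocol Synopsis (Statistical Analyses) and Protocol 10.2.1.

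The cost is a few sentences and table labels. No new model, visit, patient or decision rule is needed, and the contrasts in item 3 already come out of the planned code. The downside for the sponsor is a more modest dose-response statement.

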### 7.1 Primary Efficacy Analysis

Descriptive statistics of the percent change from baseline in LDL-C will be presented by treatment group at each visit, with the focus being on the percent change from baseline to Day 28, Day 56, and Day 84 in LDL-C, using the FAS. A longitudinal analysis will be performed with a mixed-effects model repeated measures analysis including percent change in LDL-C as the dependent variable, visit as a fixed effect and patient as a random effect. The additional drug benefit with increasing dose will be estimated from the mixed-effects model. The FAS will be used for this analysis. Least-squares mean differences and corresponding 95% confidence intervals, separately for each of the 3 paired comparisons (300 versus 600 mg, 300 versus 900 mg, and 600 versus 900 mg) will be provided.

The mixed-effect model repeated measures analysis will use an unstructured covariance matrix for the within-subject correlation; if the model does not converge with this correlation structure, an auto-regressive correlation structure will be assumed. If the model still does not converge then other covariance structures will be explored. The final correlation structure will be determined by the information criteria of Akaike and Schwarz. The data from each scheduled visit will be included in the model. Example SAS® code for performing this analysis is as follows:

```
PROC MIXED;
  CLASS SUBJID VISIT;
  MODEL PCHG = VISIT;
  REPEATED VISIT / type=UN subject=SUBJID;
  LSMEANS VISIT / cl pdiff;
RUN;
```

In addition, a scatterplot with a linear regression fit of the percent reduction from baseline versus dose will be performed.

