4.3 Withdrawal Criteria

Participation of a patient in this clinical study may be discontinued for any of the following reasons:

- The patient withdraws consent or requests discontinuation from the study for any reason;
- Occurrence of any medical condition or circumstance that exposes the patient to substantial risk and/or does not allow the patient to adhere to the requirements of the protocol;
- Any SAE, clinically significant adverse event, severe laboratory abnormality, concomitant illness, or other medical condition which indicates to the Investigator that continued participation is not in the best interest of the patient;
- Pregnancy;
- Requirement of prohibited concomitant medication;
- Patient failure to comply with protocol requirements or study-related procedures; or
- Termination of the study by the Sponsor or the regulatory authority.

If a patient withdraws prematurely from the study due to the above criteria or any other reason, study staff should make every effort to complete the full panel of assessments scheduled for the ET Visit. The reason for patient withdrawal must be documented in the electronic Case Report Form (eCRF).

In the case of patients lost to follow-up, attempts to contact the patient must be made and documented in the patient's medical records.

Withdrawn patients will not be replaced unless the number of withdrawn patients study-wide is >2 . If >2 patients are withdrawn from the study, then replacement patients will be enrolled to ensure ≥ 6 patients complete the entire study (the entire Treatment Period).

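### SAP 7.1 sets no degrees-of-freedom method, so under the auto-regressive fallback the printed 95% limits for each dose mean would cover about 92 to 94% if within-patient correlation is high (minor)

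*SAP*

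**What the plan says.** SAP 7.1 specifies a repeated-measures model of percent change in LDL-C on all scheduled visits. The code, introduced by "Example SAS® code for performing this analysis is as follows", has three lines that matter here:

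- "MODEL PCHG = VISIT", with no option after it;
- "REPEATED VISIT / type=UN subject=SUBJID", so the planned covariance is unstructured (UN);
- "LSMEANS VISIT / cl pdiff", which prints confidence limits for each visit mean as well as for the differences.

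The text itself promises "Least-squares mean differences and corresponding 95% confidence intervals, separately for each of the 3 paired comparisons" of the doses. If UN fails, "if the model does not converge with this correlation structure, an auto-regressive correlation structure will be assumed". A further sentence adds: "The final correlation structure will be determined by the information criteria of Akaike and Schwarz". Neither the SAP nor the protocol mentions a degrees-of-freedom method or a small-sample correction.

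About 8 patients are planned. Protocol 4.3 provides for replacements only so that at least 6 patients "complete the entire study (the entire Treatment Period"). Protocol 2.2 and SAP 2.1.2 call a dose effective if the mean LDL-C reduction after 4 weeks is at least 15%.

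**The concern.** With 6 to 8 patients, the t quantile depends noticeably on the degrees of freedom (df). If the code is run as written, a switch of covariance structure also switches the df from a between-patient to a within-patient count, without anyone having chosen that. A dose mean is uncertain largely because patients differ from one another. Six correlated visits per patient add much less information about it than their number suggests, so a within-patient count can overstate the precision.

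At stake is the width of the model's interval around each dose's mean LDL-C change, which a reader will set beside the 15% criterion. The interval method would also depend on a convergence result or an information criterion instead of being fixed in advance.

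**Working it through.** **Inputs from the documents.** n = 8 planned, 6 as the minimum number of completers; 6 post-baseline lipid visits (Days 14, 28, 42, 56, 70, 84; SAP 7); visit as the only fixed effect.

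**Assumptions.** The software default for a REPEATED-only model is the between-within method. Data are complete and normal. The documents give no SD or within-patient correlation ρ, so a range is shown. They also give no precision figure to reproduce: SAP 11 says only that 8 patients give reasonable precision.

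**1. Default df.**
- UN: n - 1 = 7 (n = 8) or 5 (n = 6). Simulated coverage of the dose means is 94.7 to 95.2%, so the nominal 95% is reproduced.
- Auto-regressive: 6n - 6 - (n - 1) = 5(n - 1). For n = 8: 48 - 6 - 7 = 35. For n = 6: 36 - 6 - 5 = 25.
- 97.5% t quantiles: 2.030 (35 df) against 2.365 (7 df); 2.060 (25 df) against 2.571 (5 df).

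**2. Df that the AR(1) variance estimate supports.** With complete data the visit mean has estimated variance σ̂²/n. The REML information for (σ², ρ) from n - 1 residual vectors of length 6 gives

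ν = (n - 1)[6 - 10ρ²/(1 + ρ²)].

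Example, n = 8, ρ = 0.8: 10 × 0.64/1.64 = 3.902, and 7 × (6 - 3.902) = 14.7. The simulated value is 14.6.

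**3. Coverage of the dose means with the default df.** Simulation of 40,000 trials per setting, AR(1) fitted by REML, ranges over Days 28, 56 and 84. The widening needed is t(ν)/t(5(n - 1)) - 1.

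| ρ | n | ν | widening needed | coverage, AR(1) true | coverage, compound symmetry true |
|---|---|---|---|---|---|
| 0.5 | 8 | 28.0 | 0.9% | 94.8-94.9% | 94.5-94.7% |
| 0.5 | 6 | 20.0 | 1.3% | 94.7-94.9% | 94.3-94.4% |
| 0.7 | 8 | 19.0 | 3.1% | 94.3-94.5% | 93.7-93.8% |
| 0.7 | 6 | 13.6 | 4.5% | 94.2-94.3% | 93.1-93.4% |
| 0.8 | 8 | 14.7 | 5.2% | 93.8-94.1% | 93.0-93.2% |
| 0.8 | 6 | 10.5 | 7.5% | 93.5-93.7% | 92.5% |
| 0.9 | 8 | 10.7 | 8.8% | 93.3-93.4% | 92.4-92.5% |
| 0.9 | 6 | 7.6 | 12.9% | 92.6-92.7% | 91.7-91.8% |
| 0.95 | 8 | 8.8 | 11.8% | 92.7-92.8% | not run |
| 0.95 | 6 | 6.3 | 17.5% | 91.8-92.0% | not run |

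In LDL-C terms, with an assumed SD of 15 points at a visit, n = 8 and ρ = 0.8: 15/√8 = 5.303. The half-width is 2.030 × 5.303 = 10.8 points on the default and 2.135 × 5.303 = 11.3 points on ν df.

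**4. The paired dose differences.** In the same runs they cover 94.4 to 95.4% if AR(1) is true, and 98.4 to 99.9% if compound symmetry with ρ of 0.7 to 0.9 is true.

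**5. Can the fallback occur?** With 6 complete patients the 6 × 6 residual matrix has rank 5, so UN is singular. With 7 or 8 it has full rank. Separately, UN has 6 × 7/2 = 21 covariance parameters and AR(1) has 2, so an information criterion applied across structures can select AR(1) even when UN converges.

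**6. What a better df method achieves.** Satterthwaite df were applied to the AR(1) fit itself. Kenward-Roger should agree for a visit mean in complete data, because the mean does not depend on the covariance estimate. Dose-mean coverage becomes 94.4 to 95.2% if AR(1) with ρ of 0.8 to 0.9 is true. It becomes 93.5 to 94.3% if compound symmetry is true with assumed between-patient SD 12 to 15 and within-patient SD 6 to 8 (ρ from 144/208 = 0.69 to 225/261 = 0.86).

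**The case against.** The strongest reply is that nothing promised or decided rests on these limits. Most of it stands.

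- A reader might infer that the intervals for the dose comparisons are too narrow. The documents do not support that. SAP 7.1 promises intervals for the three paired differences, and step 4 shows that these hold 95% or are conservative. They fell short (to 91.9%) only when the SD was made to rise 1.5-fold over the visits, where the Day 84 mean fell to 88.8 to 90.1%. That comes mainly from forcing one variance on all visits, not from the df.
- A reader might infer that the 15% dose decision is compromised. The criterion is a point mean with no confidence limit, and SAP 7.1 and 7.2 also plan descriptive statistics and responder counts.
- A reader might infer that the planned analysis is wrong. With complete data the UN fit is unaffected.
- The code is an example, and SAP 5.4 leaves programming specifications to separate documents. Still, it is the only specification given. Coding patient as a random effect instead would leave 48 - 13 = 35 residual df for n = 8, the same number.
- The figures for 6 patients assume that only six supply data. Early withdrawals with a valid post-baseline value stay in the Full Analysis Set (SAP 4.1.2), so these figures are the unfavourable end. The information-criterion sentence may also be meant only for structures tried after non-convergence.

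What remains is that the code prints limits for the dose means, in a path that the plan itself describes, with df that nobody chose.

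**Conclusion.** The point holds as a minor one. No df method is specified. On the software default the auto-regressive fallback gives dose means 25 to 35 df, and their 95% limits cover about 92 to 94% if within-patient correlation is about 0.7 to 0.95. High correlation is plausible, since a patient's six values share one baseline, but the documents give no value. At a true AR(1) correlation of 0.5 or less, coverage is about 95%.

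The result rests on the assumed default, on complete normal data, and on the fallback being used. The fallback is realistic with only 6 complete patients, or if the information criteria choose among all structures. It is not the expected path with 7 or 8 complete patients under the convergence rule alone. The limits feed no stated decision, but they are the model's uncertainty for the dose means set against the 15% criterion.

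**What to change.** In SAP 7.1, write `MODEL PCHG = VISIT / DDFM=KR;` (Kenward-Roger), and state that it applies to every covariance structure tried and to the secondary endpoint models. Fixing the df at n - 1 instead would over-correct: simulated AR(1) coverage of the dose means would be about 95.7 to 98.5%.

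The cost is one option. With complete data the point estimates do not change, and the UN fit keeps n - 1 df. Fallback intervals for dose means become about 3 to 12% wider at correlations of 0.7 to 0.9, more at 0.95 (up to 17.5% for 6 patients by the formula above), and about 1% wider at 0.5.

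The option should not be described as restoring 95% in all cases. The shortfall that remains if the true structure is not auto-regressive is covariance misspecification, which a df method does not remove.
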